#### 4.1 Schedule of Events

Study Day	Visit 1 Screening (-Day 20 or longer)	Visit 2 Day 1 Baseline	Visit 3 Day 8 (± 1)	Optional Visit Day 9	Visit 4 EOS Day 15 (± 2) or Early Term
Informed Consent/Assent	X				
Medical History, Demographics, Vital Signs, Height and Weight	X	Reconfirm (except height)			
Limited Physical Exam		X			
Inclusion/Exclusion Criteria	X	Reconfirm			
Urine Pregnancy Test (UPT) 	X	X	X 	X 	X
Cosyntropin Stimulation Test (CST)	X 	Confirm eligibility 	X 	X 	X 
Percent BSA Affected with Disease	Confirm eligibility	X	X		X
Investigator's Global Assessment (IGA) Score	X	X	X	X 	X 
Percent BSA to be Treated with Test Article	Confirm eligibility	X	X		
Provide (or review) Instruction Sheet to Subject and Demonstrate How to Apply the Test Article		X	X		
Provide Subject Diary to Subject and Completion Instructions		X	X		
Study Treatment (approximately every 12 hours)		X	X  (withhold AM application until after trough PK blood draw)		
Concomitant Medication Assessments	X	X	X	X 	X
Adverse Events Assessment	X	X	X	X 	X
Record Local Skin Reactions		X (pre- and post-test article application) 	X (pre- and post-test article application) 	X 	X

Study Day	Visit 1 Screening (-Day 20 or longer)	Visit 2 Day 1 Baseline	Visit 3 Day 8 (<math>\pm 1</math>)	Optional Visit Day 9	Visit 4 EOS Day 15 (<math>\pm 2</math>) or Early Term
Drug Accountability (with Weights)		X	X	X 	X 
PK Blood Draws	X		X (trough approx. 12 hours post-treatment on Day 7)	X  (trough approx. 12 hours post-treatment on Day 8)	X (trough approx. 12 hours post-treatment; Pre-CST)

1 To be performed 20 or more days prior to the Baseline visit (Day 1).

2 This visit is to take place on the day following Visit 3/Day 8.

3 If results at Final Visit show evidence of adrenal suppression, testing will be performed at 4-week intervals until adrenal axis function has normalized or stabilized.

4 Final scheduled visit occurs at Day 15  $\pm$  2.

5 All female subjects will have a UPT at Screening, Baseline and at the end of study.

7 Subjects with an abnormal CST at Screening will be discontinued from the study.

8 Subjects who have cleared their treated lesions by Day 8 (IGA score of 0) will have a CST performed on Day 8 (7AM to 9AM) and not on Day 15 with the option of having CST performed 7AM to 9AM on Day 9 if CST cannot be done on Day 8.

9 All LSRs will be assessed pre-application and only burning/stinging will be assessed post-application.

10 Weigh and collect test articles at the end of study visit.

## 5. DEFINITIONS

- The “Treatment Area” is defined as the entire body exclusive of the face, scalp, groin, axillae, or other intertriginous areas.
- End of Study (EOS) visit is the visit at which psoriasis has cleared or end of the assigned treatment period.
- A completed subject is a subject who completes the treatment as specified in the protocol and who completes the EOS evaluations.
- A subject’s psoriasis is defined as cleared if, at any visit, the investigator reports a score of zero (0) for IGA.
- Visit 1 is designated as Screening.
- Visit 2 is designated as Baseline.
- Visit 3 is designated as Day 8.
- Visit 4 is designated as Day 15.

## 6. CLINICAL EVALUATIONS

### 6.1 Investigator’s Global Assessment

The IGA score (5-point scale of 0 to 4) is an evaluation of the overall severity of a subject’s psoriasis in the Treatment Area and takes into consideration the three individual characteristics of psoriasis (scaling, erythema, and plaque elevation). At Screening, Baseline Visit/Day 1, Day 8, and Day 15/EOS, the investigator will evaluate all active psoriasis plaques that are in the Treatment Area and report the single integer score that describes the overall severity of the subject’s psoriasis using the following scale:

## **6.2 Percent Body Surface Area Affected with Disease**

This is defined as the BSA which is affected with psoriasis within the Treatment Area. The percent BSA affected with psoriasis will be estimated at the Baseline Visit/Day 1, Day 8, and Day 15/EOS.

## **6.3 Percent Body Surface Area Treated with Test Article**

This is defined as the BSA which is affected with psoriasis within the Treatment Area that will be treated. In most cases there is no difference between percent BSA affected and percent BSA treated unless the affected BSA is too large to be treated with the drug dosing limitation of 50 grams per week (e.g., 3.5 grams per application). The percent BSA to be treated will be estimated at Baseline and Day 8.

# **7. SAFETY EVALUATIONS**

## **7.1 Cosyntropin Stimulation Test**

At Visit 1 (Screening Visit, Part B), a CST will be initiated for each subject between 7 and 9AM.

At the EOS visit, a CST (and any follow-up CSTs) should be ideally initiated between 7 and 9AM but within  $\pm$  one hour of the screening CST, after confirmation that the subject has not applied test

article at least 8 hours prior to the visit. If these conditions are not met, the subject should be rescheduled for CST on the next day.

If the results of the Visit 1 (Screening) CST indicate the subject has an abnormal HPA axis response (defined as a post-stimulation serum cortisol level of  $\leq 18\mu\text{g}/\text{dL}$ ), the subject should be classified as a screen failure and withdrawn from the study.

If a subject's EOS CST results show an abnormal HPA axis response (defined as a post-stimulation serum cortisol level of  $\leq 18\mu\text{g}/\text{dL}$ ), the test article will be considered to have caused adrenal suppression in the subject. The subject will be required to return for additional follow-up visits, no less than every four weeks, until the HPA axis response has been documented to return to normal.

## **7.2 Pharmacokinetic Tests**

Blood for PK analysis will be drawn three times: at Screening (pre-application, time=0), Day 8, and Day 15 (unless IGA=0 at Day 8), approximately 12 hours after the dose on the previous day. All eligible subjects will have blood drawn at Screening for baseline drug concentration in plasma. On Day 8, all subjects, regardless of lesion clearance, will have blood drawn for assessment of trough drug concentration in plasma. At the Day 15 visit, subjects who have continued to treat lesions will have a final PK blood sample collected approximately 12 hours after their Day 14 evening application and just prior to the initiation of the CST.

## **7.3 Adverse Events**

An AE is any untoward medical occurrence associated with the use of a drug in humans, whether or not considered drug related. An AE can be any unfavorable and unintended sign (e.g., an abnormal laboratory finding), symptom, or disease temporally associated with the use of a drug, without any judgment about causality. An AE can arise from any use of the drug (e.g., off-label use, use in combination with any drug) and from any route of administration, formulation or dose, including an overdose.

The severity of an AE will be recorded as mild, moderate, or severe. The relationship between an AE and the test article will be classified as definitely related, probably related, possibly related, unlikely related, or not related.

## **7.4 Local Skin Reactions**

At all post-screening visits, the investigator or designee will observe or directly query the subject regarding LSRs known to be associated with topical application of corticosteroids. The severity of the following LSRs: telangiectasia, skin atrophy, burning/stinging and folliculitis will be recorded as 0-none, 1-mild, 2-moderate, or 3-severe. A LSR is to be recorded as an AE only if therapy or discontinuation of test article is required.

## 7.5 Urine Pregnancy Tests

A UPT will be performed on all female subjects at Visit 1 (prior to CST), Visit 2 (prior to treatment), and at EOS or if the subject withdraws prematurely.

## 8. STATISTICAL METHODS

### 8.1 General Considerations

This section presents the statistical approaches that are anticipated for the analysis of the study data. These approaches may at times require modifications due to unanticipated features of the data. Deviations from analyses summarized in this document will be noted in the CSR.

All statistical analyses and summaries will be prepared using SAS® version 9.4 unless otherwise stated.

Frequency counts and percentages will be reported for categorical data and sample size, mean, standard deviation (SD), median, minimum and maximum values will be reported for the continuous variables.

In general, all summary tables will be supported by a relevant subject data listing which will be sorted by study site, subject identification, and visit, as applicable. Figures may be created to aid in the interpretation of results.

### 8.2 Analysis Populations

#### 8.2.1 *Safety Population*

All subjects enrolled in the study who were dispensed and applied test article at least once will be included in the analysis of safety and will be considered the Safety population. Subjects will apply the initial dose of test article in the clinic on Day 1.

#### 8.2.2 *Evaluable Population*

The Evaluable population will include those subjects in the Safety population who have both Screening and EOS serum cortisol data (pre- and post-cosyntropin stimulation) and meet the following criteria:

- Meets all inclusion/exclusion criteria, including normal response to cosyntropin stimulation defined as a Screening CST with a 30-minute post-stimulation cortisol level  $>18 \mu\text{g/dL}$ .
- Screening and EOS CST were conducted between 7-9 AM.
- EOS CST was conducted within  $\pm 1$  hour of the Screening CST.
- Applied at least 80% and no more than 120% of the expected number of applications and applied the final dose no more than 14 hours prior to the start of the CST test.

- Has not taken or applied any medications that may interfere with HPA axis function.
- Do not have any other significant protocol deviations.

HPA axis suppression analysis will be conducted on the Evaluable and Safety populations.

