10. Subject is currently using a beta-blocking medication (e.g., propranolol) or angiotensin converting enzyme (ACE) inhibitors (e.g., lisinopril) at a dose that has not been stabilized, in the opinion of the investigator.
11. Subject has a history of sensitivity to any of the ingredients in the test article (see [Section 6.1](#)).
12. Subject is pregnant, lactating, or is planning to become pregnant during the study.
13. Subject is currently enrolled in an investigational drug or device study.
14. Subject has used an investigational drug or investigational device treatment within 30 days prior to Visit 1 (Screening).
15. Subject has been previously enrolled in this study and treated with the test article.
16. Subject has an irregular sleep schedule or works night shifts (cortisol levels exhibit physiological diurnal variation).
17. Subject has a screening Cosyntropin Stimulation Test (CST) with a post 30-minute stimulation cortisol level of $\leq 18 \mu\text{g/dL}$.
18. Subject is known to be noncompliant or is unlikely to comply with the requirements of the study protocol (e.g., due to alcoholism, drug dependency, mental incapacity) in the opinion of the investigator.

5.1.3 *Subject Withdrawal Criteria*

Procedures for handling subjects who are discontinued from the study are described in [Section 14.2](#). Subjects who are discontinued will not be replaced; however, enrollment will continue until at least 20 evaluable subjects are achieved.

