At Day 8, all subjects will return to the clinic for the study staff to record percent BSA affected, record percent BSA treated, IGA, review test article compliance, and collect information on AEs and LSRs. All subjects, regardless of lesion clearance, will have blood drawn on the morning of Day 8 to assess drug concentrations in plasma (trough values). Any subject who has completely cleared their treated lesions (IGA score of 0 in Treatment Area) will discontinue dosing of test article, have a CST performed between 7 and 9AM, be assessed for any AEs and LSRs, review and document any concomitant medications, and complete EOS procedures on Day 8. If CST, AEs, LSRs, concomitant medications and EOS procedures cannot be performed on Day 8, then the subject will continue dosing of test article and return on Day 9 for morning PK, CST and all EOS procedures to be performed. Subjects who are clear at Day 8, complete CST on Day 8, and have all EOS procedures completed on Day 8 will exit the study at Day 8.

Subjects who have not cleared by Day 8 will apply their morning dose at the clinic after the Day 8 trough blood sample is drawn and continue twice-daily application of the test article until Day 15. Their percent BSA affected and percent BSA treated will be

documented at Day 8. Any AEs or LSRs (i.e., burning/stinging only) post-application will be recorded.

Subjects will apply their final dose on the evening of Day 14 and record the time of the application. The final application of test article on Day 14 should be approximately 12 hours before the final PK blood is drawn on the morning of Day 15.

At Day 15, subjects who have continued to apply test article through Day 14 will return to the clinic for the study staff to collect information on AEs and LSRs, record percent BSA affected, draw a final trough PK blood sample prior to EOS CST, and perform the EOS CST. All units of test article will be collected and weighed. If any of these subjects have adrenal suppression they will be scheduled for one or more post-treatment follow-up visits.

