13. LABORATORY TESTS

13.1 Cosyntropin Stimulation Test

At Visit 1 (Screening Visit, Part B), a cosyntropin stimulation test will be initiated for each subject between 7 and 9AM.

At the End of Study visit (i.e., the visit at which psoriasis has cleared or end of the assigned treatment period), a CST (and any follow-up CSTs) should be ideally initiated between 7 and 9AM but within \pm one hour of the screening CST, after confirmation that the subject has not applied test article at least 8 hours prior to the visit.⁹ If these conditions are not met, the subject should be rescheduled for CST on the next day.

Perform the cosyntropin stimulation test as follows:

- Collect a pre-stimulation blood sample (approximately 6-7 mL) as specified in the Laboratory Manual.
- Reconstitute one vial of cosyntropin (0.25 milligrams) in sodium chloride for injection USP (the volume of sodium chloride in the package insert for Cortrosyn [[Appendix 4](#)] is 2 to 5 mL).
- Inject the cosyntropin intravenously (the length of time during which the cosyntropin should be injected is 2 minutes [[Appendix 4](#)]).
- Thirty minutes after completing the cosyntropin injection collect a post-stimulation blood sample (approximately 6-7 mL) as specified in the Laboratory Manual.

If the results of the Visit 1 (Screening) CST indicate the subject has an abnormal HPA axis response the subject should be classified as a screen failure and withdrawn from the study following the procedures in [Section 14.3](#). In addition, direct the subject to consult with their physician concerning the abnormality unless the investigator believes it is not medically indicated. The conversation with the subject must be documented in the source documents.

If a subject's end of study CST results show an abnormal HPA axis response

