13.3 Pharmacokinetic Tests

Blood (approximately 5 mL) for PK analysis will be drawn three times: at Screening (pre-application, time=0) and at Day 8 and Day 15 (unless IGA=0 at Day 8), approximately 12 hours after the dose on the previous day. All eligible subjects will have blood drawn at Screening for baseline drug concentration in plasma. On Day 8, all subjects, regardless of lesion clearance, will have blood drawn for assessment of trough drug concentration in plasma. Prior to the visit, subjects will be reminded to record i) the 12-hour “clock” time that the test article was applied in the evening of the day before the visit (Day 7) and ii) withhold application of the morning dose of test article on the morning of the visit (Day 8) until after the trough PK blood draw has been taken. Following this trough PK blood draw, subjects will apply, under supervision from the study staff, the morning dose of test article to the designated area and the time of application will be recorded and the percent BSA treated with test article and percent BSA affected will be recorded. Subjects who have cleared their treated lesions by Day 8 will not apply the Day 8 morning dose (unless CST and EOS procedures need to be performed on Day 9). At the Day 15 visit, subjects who have continued to treat lesions will have a final PK blood sample collected approximately 12 hours after their Day 14 evening application and just prior to the initiation of the CST.

All blood samples will be processed, stored and transported per the methodology provided by the analytical laboratory.

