18. STATISTICAL CONSIDERATIONS

18.1 Sample Size

Subject enrollment will continue until at least 20 subjects with both Screening and EOS serum cortisol data (pre- and post-cosyntropin stimulation) have completed the study without any significant protocol deviations (evaluable subjects). This may require the enrollment of approximately 25 subjects.

No formal power calculations were performed to establish the sample size. The number of subjects enrolled who complete the study is historically consistent with other HPA studies.

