## **8.4 Sample Size**

No formal power calculations were performed to establish the sample size. The number of subjects enrolled who complete the study is historically consistent with other HPA studies.

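### Does the SAP's stricter Evaluable population undercut the protocol's commitment to at least 20 evaluable subjects?

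*SAP*

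**What the plan says.** Protocol 5.1.3 says that "enrollment will continue until at least 20 evaluable subjects are achieved". Protocol 18.1 describes these as subjects with Screening and end-of-study (EOS) cortisol data who "have completed the study without any significant protocol deviations (evaluable subjects"), and expects to enrol about 25 to reach the number. There is no power calculation, and the protocol does not define a significant deviation.

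SAP 8.2.2 builds the Evaluable population from the Safety population. Besides paired cortisol data and eligibility, it requires that "Screening and EOS CST were conducted between 7-9 AM", that the EOS cosyntropin stimulation test (CST) fell within one hour of the Screening clock time, that 80% to 120% of expected applications were made, and that the subject "applied the final dose no more than 14 hours prior to the start of the CST test". Interfering medication and any other significant deviation also exclude.

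SAP 8.4 does not repeat the target of 20. It says only that "The number of subjects enrolled who complete the study is historically consistent with other HPA studies". SAP 9 states that the Evaluable population replaces the mITT population and that its criteria are there to make the tests comparable between subjects. It does not mention the count of 20.

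**The concern.** One word carries two definitions. A subject can follow the protocol, count toward the 20, and still be left out of the SAP's Evaluable set. The count of 20 is the trial's only sample-size commitment. If the report showed an Evaluable n of 18, a reader might not know at once whether enrolment stopped short or the stricter SAP list removed subjects who had been counted.

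The rescheduling instruction seems to add a route to exclusion. When the CST conditions are not met, protocol 13.1 says: "If these conditions are not met, the subject should be rescheduled for CST on the next day". Protocol 6.2.1 says: "Subjects will apply their final dose on the evening of Day 14 and record the time of the application". If nothing further were applied, the rescheduled test would fall outside the SAP's 14-hour limit.

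**Working it through.** **1. The stated figure.** The target of 20 has no formula behind it, so it cannot be reproduced. The step from 20 to about 25 is consistent with a 20% loss, 20 / (1 − 0.20) = 25, but the documents give no loss rate.

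**2. The two definitions side by side, for the Visit 4 test.**

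| Item | Protocol | SAP 8.2.2 |
|---|---|---|
| Screening CST clock time | 7-9 AM (10.1, 13.1) | 7-9 AM |
| EOS CST clock time | 7-9 AM preferred (10.3, 13.1) | 7-9 AM required |
| Distance from Screening clock time | ±1 hour | ±1 hour |
| Last dose to CST | at least 8 h (13.1); target about 12 h (6.2.1, 13.3) | at most 14 h |
| Applications | 80-120% for compliance and the PK population (18.3, 18.3.1) | 80-120% required |

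So three criteria are narrower or newly applied. Two examples show this. Screening at 8:45 and EOS at 9:30 are 45 minutes apart, which protocol 13.1 allows and SAP 8.2.2 excludes. A last dose at 5:30 PM before an 8:00 AM test gives 14.5 hours, above the 8-hour minimum but over the SAP limit.

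The clock-time difference is small. Screening at 7-9 AM with a ±1 hour rule allows EOS starts from 6 to 10 AM, so only starts at 6-7 AM or 9-10 AM are affected. Subjects who clear by Day 8 already have a fixed 7-9 AM window (protocol 10.3).

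**3. Can the Evaluable n fall below 20?** Yes. Let q be the share of protocol-evaluable subjects who fail the added criteria. The documents give no q, so these values are assumptions. If enrolment stopped at exactly 20, the chance of at least one exclusion is 1 − (1 − q)^20: 33% at q = 2%, 64% at 5% and 88% at 10%. At q = 0 it is zero.

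**4. What a shortfall costs.** The SAP names no interval method; exact (Clopper-Pearson) limits are assumed. With no suppressed subject the upper limit is 1 − 0.025^(1/n):

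- n = 20: 16.8%
- n = 18: 18.5%
- n = 16: 20.6%

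Near the adult lotion rate in protocol section 1 (23.8%, or 5/21), 5/20 gives 8.7% to 49.1%, a width of 40.4 points. 4/18 gives 6.4% to 47.6%, a width of 41.2 points.

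**5. Are excluded subjects lost to the reader?** No. Every protocol-evaluable subject was treated and has an EOS cortisol result, so each belongs to the Safety population. SAP 8.9.3 reports the proportion suppressed with 95% limits there too. If the protocol's count is met, that denominator is at least 20 whatever SAP 8.2.2 removes. SAP 8.5 gives the number in each population, plus subject listings of deviations and population membership.

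**6. The rescheduled test.** Assume a CST at 8 AM on Day 16. A last dose at 8 PM on Day 14 leaves 36 hours; one at 8 PM on Day 15 leaves 12 hours. Only the first breaks the 14-hour limit. Protocol 10.3 ties the final application to the evening before the next clinic visit as well as to nominal Day 14. Visit 4 has a ±2 day window, and protocol 13.3 places the last sample "approximately 12 hours after their Day 14 evening application and just prior to the initiation of the CST". The text is ambiguous about a repeat visit, but it does not establish that the subject goes undosed.

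**The case for a change.** The strongest case for acting is that the SAP reuses the protocol's word with a tighter meaning and never says so where the sample size is discussed. One exclusion is enough to bring 20 down to 19. SAP 8.5 plans no table of exclusions by criterion. Two sentences and a short count would settle it without altering any analysis set.

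The difference in wording and the silence of SAP 8.4 and 9 on the count of 20 both stand. The consequence is much weaker. The claim that a reader could not explain an n below 20 does not survive SAP 8.5, whose listings allow each subject's membership and deviations to be traced. The last bullet of SAP 8.2.2 speaks of any *other* significant deviation, which suggests that the listed criteria are partly the SAP's working definition of the term the protocol left open. On that reading, some exclusions would not have counted toward the 20 either. The 14-hour limit likewise puts a number on the protocol's 12-hour target. A note naming only CST timing and last dose would itself be incomplete, because the 80-120% rule also differs.

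Of the rescheduling argument, only the ambiguity stands. Protocol 6.2.1, 10.3 and 13.1 and SAP 7.1 and 8.2.2 must be read together and reconciled on the last dose before a repeat test. I take no view on which reading is right. The analyst applies the 14-hour criterion to the recorded dose time either way.

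**Conclusion.** No change to the plan is needed. The SAP makes a fair trade-off: it accepts a possibly smaller Evaluable set in return for cortisol tests taken under comparable conditions. It declares that choice with a reason and reports the wider Safety population beside it. The missing link to the count of 20 is a small gap that ordinary reporting of population sizes and exclusions fills.

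The number excluded is not estimable from the documents and may be zero. A loss of two from 20 would raise the exact upper limit by about 1.7 points when nobody is suppressed (16.8% to 18.5%), and would widen the interval by under one point near the adult rate (40.4 to 41.2). No hypothesis test, power or error rate is involved. SAP 9 says in the past tense that some planned data were not captured. This suggests data collection was over when the SAP was written, in which case an added caveat could not have altered enrolment.

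The conclusion rests on three assumptions: exact confidence limits, a loss of only a few subjects, and the Safety-population result and the SAP 8.5 listings being produced as planned. A sentence in the report naming all three narrower criteria would be helpful but optional. It would change no estimate and no conclusion.
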